4.5.2 Consent for Patient Participants

Individual participant informed consent will be taken for participation in the trial. Participants are consenting to receive their rehabilitation using the assigned approach (ILA or standard care), and for collection of data, and completion of additional assessments.

The Easy Read version of the PIS will be used to facilitate a conversation with any potential participant who finds the format of the standard PIS difficult to follow/digest. It is intended as a conversation support tool, to ensure that information about the trial is available in an accessible format for all patients, but particularly those with an impairment of communication or cognition.

All new stroke admissions will be screened for eligibility within 72 hours of admission. Those that meet the criteria will be provided with verbal and written information, which they will be given 24 hours to consider. Those willing to participate will be asked to sign a consent form.

There may be individuals who do not meet the inclusion criteria at the beginning of their Stroke Unit stay, but regain enough function to meet the criteria at a later date. We will continue to monitor potential participants, and will recruit up to 14 days post stroke, if eligibility changes.

The process of recruitment and consent will be led by the research practitioner(s) at each site. Recruitment will take place across an approximate period of four-months at each Unit.

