4.5.3.3 Process if a participant regains capacity during the study

It is feasible that a participant who did not have capacity to provide informed consent at the beginning of the study, regains the ability to do so at some point during the study. The therapists who are delivering the treatment interventions, as well as the research team, will be briefed with regards to this. They will be asked to inform the Research Practitioner and local PI if they feel that a participant's ability to consent has changed. This will then be reassessed. If, at this point, the person is deemed to have capacity to make a decision regarding participation in the research, they will be provided with the study information and will be supported to make this decision. If they opt to withdraw from the study, they can do so, without consequence. Data collected up to this point will be included in the final analysis, unless the individual explicitly asks for it not to be.

Therefore, the Consultee Declaration only applies for as long as the participant lacks capacity. Stroke teams manage issues relating to capacity on a frequent basis, and are therefore typically very aware of the principles of the Mental Capacity Act, capacity assessments and informed consent.

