4.10 Training for Intervention Sites

For sites randomised to the intervention arm, all physiotherapists, occupational therapists and therapy assistants will be trained in the ILA. Training is anticipated to last no more than 3 hours. Additional training sessions will be offered if new members join the team during the recruitment phase. A manual including written, photographic and video resources will demonstrate how to adapt standard care interventions to the ILA. Therapists will be able to refer to the manual throughout their involvement in the study.

Whilst the wider multidisciplinary team (e.g. nurses, doctors, other AHP's) will not specifically be asked to change their approach with patients, those at intervention sites will be invited to attend a short education session to raise their awareness of the trial, and will be provided with written information about the study, and the concepts under investigation. As these professions wouldn't typically be analysing movement or giving specific instructions/feedback, this level of engagement is deemed appropriate and realistic.

The therapy team will be encouraged to give the MDT (particularly nurses) specific guidance about how to instruct an individual patient during movement (as part of a manual handling care plan, and in line with the ILA approach). These awareness raising sessions will support the MDT to understand and follow through these instructions.

As part of the training, clinical staff will be reminded of the options to withdraw participants from the study, should there be concerns about the impact the ILA has on their recovery (see 7.1.1).

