4.12 Measures

Measures will be performed and recorded by the stroke research practitioner(s), or designated clinician, at each site. As the research practitioner will not be blind to the intervention arm, all measures will be video recorded, and later scored by a blinded second assessor. Frequent measures are required to understand *rate* of change. Outcome measures have been selected with consideration of international recommendations for measurement of sensorimotor recovery in stroke [12].

At baseline:

- Movement Specific Reinvestment Scale (Self-Report Questionnaire) (MSRS)

At baseline, week 2, week 4, week 6 post enrolment (or up to the point of discharge):

- Fugl Meyer – motor leg sub section
- Modified Postural Adjustment in Stroke Scale (SwePASS)
- Modified Rivermead Mobility Index (mRMI)
- Able to sit for 1 minute unsupported?
- Able to transfer from bed to chair independently?
- Able to walk 10m independently?

At point of discharge

- Discharge destination and care requirements immediately on discharge (number of care visits per day multiplied by the number of carers required)
- Fugl Meyer – motor leg sub section
- Modified Postural Adjustment in Stroke Scale (SwePASS)
- Modified Rivermead Mobility Index (mRMI)
- Able to sit for 1 minute unsupported?
- Able to transfer from bed to chair independently?
- Able to walk 10m independently?
- Movement Specific Reinvestment Scale (MSRS)

At 3 months post enrolment:

- Fugl Meyer – motor leg sub section
- Modified Postural Adjustment in Stroke Scale (SwePASS)
- Modified Rivermead Mobility Index (mRMI)
- Able to sit for 1 minute unsupported?
- Able to transfer from bed to chair independently?
- Able to walk 10m independently?
- Modified Rankin Scale (mRS)
- EQ-5D
- Movement Specific Reinvestment Scale (MSRS)

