7.1 Assessment of Safety

7.1.1 Expected ILA Adverse Events

Although unlikely, there is a possibility that the ILA is perceived as less personal/motivating for patients, and this may be associated with a reduced willingness to participate in therapy. We will monitor adherence with rehabilitation across all sites. Non-compliance will be considered an AE if (i) a patient is declining to participate in rehabilitation sessions over a period of 5 days and (ii) the clinical team are unable to account for this in any other way. This will be addressed on an individual basis through discussion with the patient and the clinical team. If indicated, they will be withdrawn from the study.

If the treating team have any concerns about using the ILA with an individual patient, for example, should they feel that a patient is not responding /recovering as expected, they should discuss this with the Chief Investigator. If indicated, the participant will be withdrawn from the study, and their rehabilitation will revert to standard care. This decision will be taken on an individual basis, following discussion with the clinical team, Chief Investigator and (if appropriate) the participant. Withdrawal due to unanticipated/unexplained lack of progress in rehabilitation will be considered an AE.

It is important to note that, whilst therapists at the intervention sites are encouraged to adhere as much as possible to the ILA guidance, this is a pragmatic trial, and they can use their own clinical judgement during each individual treatment session. This is monitored as part of the feasibility aspect of this trial.

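### The lack-of-progress withdrawal in Section 7.1.1 is from the study, is written only for ILA sites, and has no stated follow-up afterwards, so outcome-related loss can differ between arms

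*Combined protocol and SAP*

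**What the plan says.** **The ILA-specific route.** Section 7.1.1 covers teams with concerns about using the ILA in a given patient, for instance "should they feel that a patient is not responding /recovering as expected". After discussion with the Chief Investigator, "If indicated, the participant will be withdrawn from the study, and their rehabilitation will revert to standard care". One sentence thus joins a change of treatment to departure from the study. Section 4.10, on training for intervention sites, adds that "clinical staff will be reminded of the options to withdraw participants from the study" and refers back to 7.1.1. Section 7.1.1 also says: "Withdrawal due to unanticipated/unexplained lack of progress in rehabilitation will be considered an AE". That sentence names no arm, but no control-unit procedure leads to it.

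**Routes open in both arms.** Section 4.14 withdraws participants after significant clinical deterioration and records the reasons. Section 4.5.3.4 withdraws those who lose capacity through a further stroke or other medical event. The non-compliance rule in 7.1.1 is monitored at all sites and can also end in withdrawal.

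**Data at and after withdrawal.** The only statement on data is in Section 4.5.3.3, for people who regain capacity and opt out: "Data collected up to this point will be included in the final analysis", unless they object. It concerns data already held. Consent in Section 4.5.2 is to the assigned approach "and for collection of data, and completion of additional assessments", so treatment and data collection are listed as separate items.

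**Use of the outcomes.** The Synopsis names 4-week change in the modified Rivermead Mobility Index (mRMI) as primary outcome. It lists retention and an effect size for a later sample size calculation among the objectives. Section 4.16 defines retention by the 4-week measures and estimates differences in Fugl Meyer, SwePASS and mRMI with confidence intervals. It names no analysis set or missing-data method.

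**The concern.** Stopping the ILA can only happen where the ILA is given. Leaving follow-up need not go with it, but Section 7.1.1 ties the two together. The patients removed are selected on recovery judged disappointing by staff who know which approach they are delivering. If their later outcomes are not collected, the ILA mean is taken over a group from which some patients seen as doing poorly have gone, with no equivalent removal in the control arm.

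Two pilot objectives are exposed. The effect size passed to Phase III could be too favourable. The 4-week ILA retention figure would count a patient who stopped the ILA before week 4 as lost to follow-up, although stopping the treatment and refusing or missing assessment say different things about feasibility. The later course of the patients in whom staff thought the ILA was not working is also useful information for a pilot, and it cannot be recovered afterwards if it is not collected.

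**Working it through.** **1. The plan's own figure.** Section 4.13 gives 60 participants in 6-8 clusters: 60/6 = 10 and 60/8 = 7.5 per cluster, which agrees with the stated 7-10. The plan gives no SD, intracluster correlation (ICC), dropout rate or expected number of ILA withdrawals, so what follows is illustration on assumed inputs.

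**2. Size of the ILA arm.** Assume 30, half of 60. Section 5.2 implies four intervention sites, and 4 × 7.5 = 30.

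**3. Shift in the ILA mean.** Suppose k of 30 ILA patients, those with the poorest perceived progress, leave before the assessment. With a normal outcome, p = k/30, and correlation r between perceived progress and outcome:

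shift in SD units = r × φ(z_p) / (1 − p)

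| k of 30 | r = 0 | r = 0.2 | r = 0.5 | r = 1 |
|---|---|---|---|---|
| 1 | 0 | 0.015 | 0.038 | 0.077 |
| 2 | 0 | 0.028 | 0.069 | 0.139 |
| 3 | 0 | 0.039 | 0.097 | 0.195 |
| 6 | 0 | 0.070 | 0.175 | 0.350 |

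For k = 3 and r = 1: φ(−1.28)/0.9 = 0.1755/0.9 = 0.195. Simulated arms of exactly 30 give slightly smaller values at r = 1: about 0.07, 0.13 and 0.19 for k = 1, 2 and 3.

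**4. Do the shared routes cancel it?** Assume both arms also lose their poorest 10% through the common rules, and the ILA arm loses 3 more (20% in all). At r = 1 the difference is 0.350 − 0.195 = 0.155 SD; at r = 0.5 it is 0.077 and at r = 0.3 it is 0.046. The shared routes reduce the asymmetry but do not remove it.

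**5. Scale of random error.** With 30 per arm, the 95% CI half-width for the difference is:
- Unclustered: 1.96 × √(2/30) = 0.51 SD.
- Clustered: t(0.975, clusters − 2) × √[(2/30)(1 + (m − 1) × ICC)], with equal arms and cluster sizes and an assumed ICC of 0.01-0.05. Eight clusters (m = 7.5, t on 6 df = 2.447) give 0.65-0.73 SD. Six clusters (m = 10, t on 4 df = 2.776) give 0.75-0.86 SD.

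Section 4.16 takes the individual patient as the unit of analysis and states no cluster adjustment, so both versions are shown.

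**6. Retention.** Only if the withdrawals precede week 4, and with no other loss, ILA retention becomes 29/30 = 97% (k = 1) to 27/30 = 90% (k = 3). Otherwise it is unchanged.

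**7. Direction.** Losing patients perceived as recovering poorly would probably raise the ILA mean. This is not certain, because the trigger is a shortfall against expectation rather than the lowest score, and these patients go back to standard care. At 4 weeks a second process operates: Section 4.12 schedules the week 2, 4 and 6 measures "or up to the point of discharge", so patients discharged early also drop out of that assessment. The net direction there cannot be stated. The 3-month assessment carries no such limit, so the mechanism is clearer at that point.

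**The case against.** A reader might infer that outcome-related loss can arise in the ILA arm alone. The documents do not support that: Sections 4.14 and 4.5.3.4 and the non-compliance rule in 7.1.1 can each remove poorly recovering patients from either arm. What remains is one additional route on one side.

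A reader might also infer that recovery after such a withdrawal is definitely not measured. The text does not say so. It is silent, and the trial flowchart (Section 4.6) and the CONSORT diagram cannot be read in the available copy. Loss of later outcomes is the ordinary reading of withdrawal from the study, not an established fact.

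Several features limit the problem:
- Withdrawal is discretionary and needs discussion with the Chief Investigator.
- Therapists have room to adapt without withdrawing anyone, since "they can use their own clinical judgement during each individual treatment session".
- Reasons for withdrawal are recorded, and unexplained lack of progress counts as an adverse event, so these cases can be counted and separated in the retention figure.
- Section 7.1.2 records adverse events to discharge and states no exception for withdrawn patients.
- The pilot's analysis is mainly descriptive, and no hypothesis test depends on the result.

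All of this stands. It lowers the likely frequency and the severity, but knowing how many patients left and why does not supply their later scores.

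The illustration should not be read as a ceiling. Three withdrawals is an arbitrary choice: six with r = 1 would give 0.35 SD, or 0.35/0.51 = 69% of the unclustered half-width. Equal arms is also an assumption; four ILA sites out of six would give about 40 against 20 patients and a half-width of 1.96 × √(1/40 + 1/20) = 0.54 SD before clustering.

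**Conclusion.** The point holds in this form: the lack-of-progress withdrawal in 7.1.1, repeated in 4.10, is from the study, is written only for ILA sites, and has no readable provision for outcomes afterwards. Outcome-related loss can therefore be differential, with consequences for ILA retention and for the effect size intended for Phase III.

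Its size is unknown. It is zero if no one is withdrawn this way, if staff judgement is unrelated to outcome or, for the 4-week figures, if all such withdrawals come after week 4. With 30 ILA patients, 1-3 withdrawals before the assessment and a normal outcome, the shift is about 0.04-0.10 SD at r = 0.5 and 0.08-0.20 SD at r = 1, and larger with more withdrawals. Random error dominates in that range (half-width about 0.5 SD unclustered, 0.65-0.86 SD under the clustered assumptions), but the confidence interval does not reflect the shift. The direction is probably in favour of the ILA at 3 months and unknown at 4 weeks. Severity is minor to moderate; the case for acting is that the remedy is cheap and uncollected outcomes cannot be recovered later.

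**What to change.** In Sections 7.1.1 and 4.10, distinguish a participant who stops the ILA from one who withdraws from follow-up. State that:

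- participants who stop the ILA keep the outcomes already scheduled in Section 4.12, unless they (or their consultee, where a declaration applies) decline or assessment is not clinically appropriate;
- they are analysed in the arm of their Stroke Unit;
- ILA stops are reported separately from loss to follow-up, using the reasons already recorded under Section 4.14.

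Reconcile the wording with Sections 4.14 and 4.5.3.4, and check that the flowchart and CONSORT diagram agree. Nothing here alters any clinical rule on when to stop the ILA or revert to standard care; those decisions stay where the protocol puts them.

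The cost is a few sentences and a consistency check. The downside is a few already scheduled assessments in patients no longer receiving the ILA. Section 4.5.2 already lists data collection and assessments separately from the assigned approach, so continued follow-up fits the way consent is described.

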4.8 Control

Standard care, as per usual working practice for the stroke unit. Control stroke units will have minimal contact with the research team, other than for data collection. They will be aware of the broad aims of the study, but not the specific detail of the intervention.

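### Section 7.1.1 counts withdrawal for unexplained lack of progress, not the lack of progress itself, so the adverse-event data on it would be one-sided

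*Combined protocol and SAP*

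**What the plan says.** Section 7.1.1, on expected adverse events of the ILA, describes two concerns.

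The first is reduced willingness to take part in therapy. Adherence is monitored at every site. Non-compliance becomes an adverse event when a patient declines sessions over 5 days and the team has no other explanation. Withdrawal may follow, but it is not part of the definition.

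The second is a patient who is not recovering as expected. This route opens with "If the treating team have any concerns about using the ILA with an individual patient", and the team then discusses the case with the Chief Investigator. The possible result is that "the participant will be withdrawn from the study, and their rehabilitation will revert to standard care". On how this is decided: "This decision will be taken on an individual basis, following discussion with the clinical team, Chief Investigator and (if appropriate) the participant". The adverse-event rule follows: "Withdrawal due to unanticipated/unexplained lack of progress in rehabilitation will be considered an AE".

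Section 4.10 adds that staff trained at intervention sites are reminded that they can withdraw participants "should there be concerns about the impact the ILA has on their recovery". For the other arm, section 4.8 says: "Control stroke units will have minimal contact with the research team, other than for data collection".

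**The concern.** The possible harm is that a patient fails to progress for no apparent reason. The rule counts what staff do about it. An ILA participant with an unexplained plateau who is kept in the trial generates no adverse event of this kind. A control participant with the same plateau has no described route to one, being already on standard care.

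This is one of only two ILA-specific concerns that section 7.1.1 names. If the pilot's adverse-event data are summarised by arm, this item could appear only under the ILA even if plateaus were equally common in both arms. It could also understate how often they occurred within the ILA arm. The synopsis makes testing the integrity of the protocol part of the primary objective and informing a Phase III trial a secondary one. An event definition that works in only one arm should be found and corrected at this stage.

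**Working it through.** The plan gives no figure to reproduce on this point. The check sets the rules side by side, followed by an illustration.

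**Step 1: is there any other route by which lack of progress is recorded as an adverse event?**
- 4.5.3.3 and 4.5.3.4 (regaining or losing capacity): withdrawal by choice, for unwillingness, or after a further medical event. Lack of progress is not covered.
- 4.8 (control): usual practice, with no lack-of-progress route described.
- 4.14 (premature withdrawal): applies to significant deterioration, with reasons recorded. Failure to progress is not mentioned, and the withdrawal is not called an adverse event.
- 7.1.2 (stroke-related events): lack of progress is not on the list. The stated recording period, consent to hospital discharge, is given for that list only; 7.1.1 states no period.
- 7.1.3 (serious events): an extreme case might qualify as significant disability or as medically significant, but this is no rule for recording an unexplained plateau.

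No other route is given.

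**Step 2: compare the two events inside 7.1.1.**
- Non-compliance: defined by what the patient does; monitored at all sites; withdrawal is a separate, later step.
- Lack of progress: defined by the withdrawal; triggered by concern about the ILA; ends in return to standard care; no threshold.

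**Step 3: apply the rule to three participants with the same flat mobility course and no explanation for it.**
- ILA, team raises a concern, participant withdrawn: 1 event.
- ILA, team carries on or adapts sessions by clinical judgement: 0 events.
- Control: 0 events.

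**Step 4: illustration.** Only the total of 60 participants (section 4.13) comes from the documents. Assumptions: an equal split, so n = 60 / 2 = 30 per arm; the same true rate p of unexplained lack of progress in both arms, 10% to 20%; and a share w of ILA cases withdrawn, 25% to 75%.
- True cases per arm = n × p: 30 × 0.10 = 3 to 30 × 0.20 = 6.
- Recorded in ILA = n × p × w: 30 × 0.10 × 0.25 = 0.75 to 30 × 0.20 × 0.75 = 4.5.
- Recorded in control: 0, on the reading reached in Steps 1 and 2.
- Share of ILA cases unrecorded = 1 − w: 25% to 75%.

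The range shows how the rule behaves. It is not an estimate for this trial.

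**The case against.** The strongest reply is that recovery is judged by the outcome measures, not by an adverse-event count. Section 4.12 schedules the mRMI, Fugl Meyer, SwePASS and three functional milestones in both arms at baseline, weeks 2, 4 and 6 (or up to discharge), at discharge and at 3 months. Scoring is from video by a blinded assessor, and the section explains: "Frequent measures are required to understand *rate* of change". Section 4.16 plans differences and effect sizes with confidence intervals for the three scales. A reader might infer from 7.1.1 that the pilot can say nothing about whether the ILA impairs recovery. The documents do not support that: slower recovery under the ILA could show in these scores, within the precision that 60 participants in 6-8 clusters allow. This part of the reply stands.

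Further points in the plan's favour:
- The adverse-event sentence names no arm. A reader might say that the text expressly sets the control count to zero. It does not; the restriction is inferred from heading, trigger and consequence. The inference is strong, because no other section supplies a control route.
- The analysis is mainly descriptive and no formal comparison of adverse events is planned, so no test is affected.
- Logging such a withdrawal as an adverse event is a cautious way to ensure it is seen, and 4.14 already records reasons for withdrawal.
- The rates in the illustration are assumed. With equal true rates assumed, it follows that any recorded difference comes from the rule.

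These points limit the consequence. They do not remove the defect: one of two events in the same section is counted at all sites and by what the patient does, and the other is not.

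**Conclusion.** The point holds as a defect in how an event is defined and recorded. On the natural reading of 7.1.1, adverse-event data on unexplained lack of progress would be effectively absent in control and dependent on discretionary withdrawal in the ILA arm. The damage is to the safety description and to its use for Phase III planning.

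The definition does not bias the planned mRMI, Fugl Meyer and SwePASS estimates. Whether withdrawn participants go on contributing outcome data is a separate question.

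The size of the distortion cannot be computed from the documents. The conclusion assumes that the lack-of-progress route is meant for ILA participants only. If control sites were meant to be covered, the text needs to say so, and the dependence on withdrawal would still remain. It is worth correcting, but it does not undermine the pilot.

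**What to change.** In section 7.1.1:
- Define unanticipated or unexplained lack of progress as the recorded event, separate from any withdrawal.
- Record it at all sites on the same basis and over the same stated period, as the section already does across sites for non-compliance.
- Report it by arm, with the number of participants and of assessment intervals observed. Inpatient assessments stop at discharge and may stop at withdrawal, so the opportunity to be flagged can differ between arms.
- Report withdrawals for lack of progress separately, with the reasons that 4.14 already collects.

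A supporting summary could be derived from the serial blinded scores. The investigators should set its threshold, and it should be presented as descriptive, not as the definition of the adverse event. A simple rule of no gain in score would ignore whether the course was expected, would flag people near the top of the mRMI (maximum 8 items × 5 = 40), and relies on scores that may be missing after withdrawal or discharge.

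The clinical decision to withdraw is unchanged. While this section is open, the statement in 7.1.3 that no adverse events are expected should be reconciled with the headings of 7.1.1 and 7.1.2.

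Cost: a wording change, a small amount of extra recording at control sites, and some subjective or noisy flags.
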